9.5. Single reference safety document

The latest version of the LPD of BESPONSA® will serve as the SRSD during the course of the study, which will be used by Pfizer to assess any safety events reported to Pfizer Safety by the investigator during the course of this study.

The SRSD should be used by the investigator for prescribing purposes and guidance.

10. PLANS FOR DISSEMINATING AND COMMUNICATING STUDY RESULTS

For the first 2 years, 6-month reports will be submitted to MFDS (i.e., reports 1-1, 1-2, 2-1, and 2-2). Thereafter, data collected in the 3rd, 4th, and 5th year will be reported to MFDS annually. Final study report (i.e., re-examination report) will be submitted to MFDS in the 6th year to include all data collected during the whole study period.

COMMUNICATION OF ISSUES

In the event of any prohibition or restriction imposed (e.g., clinical hold) by an applicable Competent Authority in any area of the world, or if the investigator is aware of any new information which might influence the evaluation of the benefits and risks of a Pfizer product, Pfizer should be informed immediately.

In addition, the investigator will inform Pfizer immediately of any urgent safety measures taken by the investigator to protect the study patients against any immediate hazard, and of any serious breaches of this NI study protocol that the investigator becomes aware of.

11. PUBLICATION OF STUDY RESULTS

Pfizer fulfils its commitment to publicly disclose study results through posting the results of this study on www.clinicaltrials.gov. Pfizer posts the results of all studies that it has registered on ClinicalTrials.gov regardless of the reason for registration.

The results are posted in a tabular format called Basic Results.

- Basic Results are due within one anniversary year of the PCD and/or LSLV.
- When PCD and LSLV are not the same date, Basic Results are posted one anniversary year from the PCD and the record is updated one anniversary year from the LSLV. The PCD cannot occur after the LSLV.

APPENDIX 1. RESPONSE CRITERIA

APPENDIX 1. RESPONSE CRITERIA

Response Criteria is defined according to 'NCCN Guideline Version 2.2016 Acute Lymphoblastic Leukemia⁹'.

The below outcome definitions will be used for reporting of response assessments.

Response Criteria for Blood and Bone Marrow:

- Complete response (CR)
 - No circulating blasts or extramedullary disease
 - No lymphadenopathy, splenomegaly, skin/gum infiltration/testicular mass/central nervous system involvement
 - Trilineage hematopoiesis and < 5% blasts
 - Absolute neutrophil count (ANC) > 1000/microL
 - Platelets > 100,000/microL
 - No recurrence for 4 weeks
- CR with incomplete blood count recovery (CRi)
 - Meets all criteria for CR except platelet count and/or ANC
- Refractory disease
 - Failure to achieve CR at the end of induction
- Progressive disease
 - Increase of at least 25% in the absolute number of circulating or bone marrow blasts or development of extramedullary disease
- Relapsed disease
 - Reappearance of blasts in the blood or bone marrow (>5%) or in any extramedullary site after a CR

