7.2.3. Duration of the study

According to MFDS re-examination regulation, the re-examination report based on collected data of 6 years must be submitted to MFDS within 3 months after the end of specified re-examination period (from the product approval date to 6 years afterwards).

The data collection period of this study is until the required subject number (100 patients) is collected. The observation period for each subject is from initiating administration of first dose of BESPONSA® to the end of the observation period of the study, which must include at least 28 calendar days following the last administration of a BESPONSA®. In case of patient that Hematopoietic Stem Cell Transplant (HSCT) after administrated BESPONSA®, follow-up until 180 days after transplantation. All the data collected during the observation period should be recorded in the case report form (CRF). In case of an adverse event/safety event recognized after the observation period ends, it should be recorded in the CRF as specified in Section 7.

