7.3.6. Administration status and response evaluation for each cycle of BESPONSA®

Record the following with regard to administrative status and response evaluation for each cycle. Record administrative status of all cycle until the last administration dose. Refer to LPD for posology and method of administration.

- Administration date

- Body surface area
- Administration dose
- Pre-medication: If 'conducted', record the detailed information in '4.Concomitant medication' clause in CRF.
- Response evaluation after each cycle: Record the evaluation date and response. Select one among 'CR', 'CRI', 'refractory disease', 'progressive disease', or 'relapsed disease'. Response Criteria is defined according to *NCCN Guideline Version 2.2016 Acute Lymphoblastic Leukemia*⁹. Refer to Appendix 1 for detailed Response Criteria. If response evaluation is not done, check 'undone' and leave the evaluation date blank.

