8.2.3.1 Response evaluations

The following response evaluations after each cycle and the final effectiveness evaluation shall be summarized using the number of subjects(n) and percentage (%).

- Response:
 - CR | CRI | Refractory disease | Progressive disease | Relapsed disease
- Effective: CR, CRI
- Ineffective: Refractory disease, Progressive disease, Relapsed disease

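### The response categories in Protocol Appendix 1 are not mutually exclusive: a CRi patient also meets refractory disease, no rule decides between them, and the SAP counts one as Effective and the other as Ineffective.

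*Protocol*

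**What the plan says.** Protocol Appendix 1 sets the definitions used to report response.

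- CR includes the condition "No recurrence for 4 weeks".
- CRi is "Meets all criteria for CR except platelet count and/or ANC", so it keeps the four-week condition.
- Refractory disease is "Failure to achieve CR at the end of induction".
- Relapsed disease is "Reappearance of blasts in the blood or bone marrow (>5%) or in any extramedullary site after a CR".

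Protocol 7.3.6 asks for a dated response after every cycle: "Response evaluation after each cycle: Record the evaluation date and response". The investigator picks one of CR, CRi, refractory, progressive or relapsed disease, or marks the evaluation as not done. Protocol 7.3.7 asks for one further choice from the same five once all cycles are finished, with no day or window. Under Protocol 7.2.3 the observation period "must include at least 28 calendar days following the last administration"; transplanted patients are followed to 180 days after transplantation.

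SAP 8.2.3.1 places CR and CRi under Effective and the rest under the other heading: "Ineffective: Refractory disease, Progressive disease, Relapsed disease". The same split defines last effectiveness (8.2.3.2) and best overall response (8.2.3.5, the first section with that number), and feeds their factor analyses (8.2.3.3 and 8.2.3.6). In the PFS section, which is also numbered 8.2.3.5, the event is the earliest of death, refractory, progressive or relapsed disease. DoR runs from first response to that PFS event.

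**The concern.** Five categories from which one must be chosen should not overlap, and should cover every evaluated patient at every time they are used. These do neither. One marrow and blood-count result can be recorded correctly, on the text, as CRi or as refractory, and the two fall on opposite sides of the only binary effectiveness outcome. An evaluated patient with stable or falling blasts after an early cycle is forced into a category meant for the end of induction, and the survival-type analyses then treat that entry as failure.

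Response is the sole effectiveness information in the analyses for the regulator (SAP section 9, Section I, Tables 31 to 39). Investigators record it at several centres, so different readings of the appendix would appear as differences in effectiveness.

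**Working it through.** The documents state no response rate or CRi share, and the basis for 100 patients is redacted, so there is no figure of the plan's own to reproduce. The check sets the definitions side by side and adds a day count.

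**1. CRi against refractory.** CRi means every CR criterion is met except platelets and/or ANC, so CR is not achieved. Refractory requires only that CR is not achieved at the end of induction. At that time every CRi patient satisfies both. Protocol 7.3.6 and 7.3.7 allow one choice, and no section gives an order of precedence.

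**2. Effect on the Effective rate.** Let n be the effectiveness set, with a patients in CR and b in CRi.

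- CRi kept as CRi: rate = (a + b)/n
- All CRi entered as refractory: rate = a/n
- Difference = b/n, the CRi proportion

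To show the mechanics only, assume n = 100 and a = 40, with exact Clopper-Pearson 95% intervals (SAP 8.1.3):

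| Assumed CRi | Rate, CRi Effective | Rate, CRi as refractory |
|---|---|---|
| 10 | 50% (39.8 to 60.2) | 40% (30.3 to 50.3) |
| 20 | 60% (49.7 to 69.7) | 40% (30.3 to 50.3) |
| 30 | 70% (60.0 to 78.8) | 40% (30.3 to 50.3) |

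The counts are assumptions and the right-hand column is the extreme case. For best overall response, reaching it would need the refractory entry at every evaluation of those patients.

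**3. Early-cycle non-remission.** Take an evaluated patient after cycle 1 whose blasts persist without a 25% rise, with no new extramedullary disease and no previous CR on BESPONSA. CR and CRi fail on blasts, progressive disease fails on the rise, and relapsed disease fails for want of a previous CR. Only refractory is left. Let its date be d1, and let CR be recorded after cycle 2 at d2 > d1.

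- Best overall response: Effective
- PFS: event at d1, before the response
- DoR = d1 − d2 < 0

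**4. Recurrence after CRi.** Relapse requires a previous CR. A patient whose only remission was CRi does not meet that wording when blasts return.

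**5. Four-week condition.** A response first documented d days after the last dose completes 28 days without recurrence at day d + 28. Within the guaranteed minimum this requires d + 28 ≤ 28, that is d ≤ 0.

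| d (days) | Confirmed at day | Beyond the 28-day minimum |
|---|---|---|
| 0 | 28 | 0 |
| 1 | 29 | 1 |
| 7 | 35 | 7 |
| 14 | 42 | 14 |
| 28 | 56 | 28 |

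The values of d are illustrative, because Protocol 7.3.7 gives no timing.

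**The case against.** The strongest reply is that the intent is clear enough. CRi has its own box on a single-choice form, and the SAP places CRi under Effective throughout, so most investigators will enter CRi. If the end of induction is undefined, a literal reader could not establish refractory at a cycle evaluation either. The definitions come from a named guideline, the study is descriptive with no formal hypothesis (SAP section 4), and Protocol 7.9 says that regulation, not the disease, shaped the design.

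Much of this stands. The separate CRi box makes wholesale miscoding unlikely. However, intent is not a stated rule. The undefined end of induction does not remove the problem, because the form offers refractory after every cycle. Descriptive aims lower the stakes but do not make the categories exclusive.

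A reader might also infer four stronger things, none of which the documents support:

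- **That Appendix 1 cannot be applied.** A response from an earlier cycle can be confirmed at a later one, and data come from the chart, so entries need not be fixed on the day.
- **That observation stops 28 days after the last dose.** Protocol 7.2.3 and 9.2 set a minimum, and nothing says how many patients stop there.
- **That transplanted patients' remissions are judged on better evidence.** No response evaluation is scheduled during their 180 days, and the final evaluation follows the last cycle for everyone. The SAP brings later disease assessments into PFS and DoR, not into last effectiveness.
- **That the effective rate moves by a particular number of points.** This would need a CRi share and a miscoding frequency, and the documents give neither.

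**Conclusion.** The point holds as a defect of definition. On the text, CRi and refractory overlap at the end of induction, and the SAP separates them into Effective and Ineffective without a precedence rule. Early-cycle non-remission has no category but refractory, which can place a PFS event before the first response and make DoR negative. The status of the four-week condition at an evaluation is unstated, and it cannot be met within the minimum observation for a response first documented after the last dose.

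The size cannot be derived. For the overlap, the shift in the Effective rate is bounded above by the CRi proportion. The number of patients affected through PFS, DoR or the four-week condition is unknown. The conclusion rests on reading the definitions as written; the cited guideline was not consulted. This is a reproducibility problem in the effectiveness outcomes, not a safety matter, and should be settled before the final analysis.

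**What to change.** 1. In Appendix 1 and the SAP, define refractory disease as failure to achieve CR or CRi, state that CRi takes precedence, and let relapse follow either CR or CRi.
2. In the SAP, do not count a cycle-level refractory entry as a PFS or DoR event when CR or CRi is recorded at a later BESPONSA cycle. Tabulate it as not effective at that cycle.
3. State that cycle and final entries are the status on the evaluation date. Report separately how many CR and CRi patients had a later evaluation, at least 28 days on, without recurrence.
4. Query existing refractory entries against the chart for CRi.

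No new CRF category is needed; with data collection planned to end on 2 January 2025 (Protocol section 4), adding one late would mix two coding schemes. The cost is wording changes and a small query round. The definitions depart slightly from the cited guideline, and PFS and DoR event dates change for the affected patients. Because rule 2 depends on later entries, it should be fixed in the SAP before the analysis is run.

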1. AMENDMENTS FROM PREVIOUS VERSION(S)

- Rationale and Background is updated according to protocol amendment 4.
- CCI
- Analysis about best overall response is added to Effectiveness analyses section.
- Analysis for publication is added to effectiveness analyses section.

2. INTRODUCTION

Note: in this document, any text taken directly from the non-interventional (NI) study protocol is *italicised*.

Rationale and Background

Acute lymphoblastic leukemia (ALL) is a rare, serious, and life-threatening condition with a need for improved therapies. Relapsed or refractory B-cell ALL is a fatal disease with a median survival time in adults of only approximately 3-6 months. The age adjusted incidence rate of ALL in the United States is 1.7 per 100,000 individuals per year, with approximately 6,020 new cases and 1,440 deaths estimated in 2014. While the cure rates and survival outcomes for B-cell ALL have improved during the last several decades, most of the improvements have occurred in younger patients, primarily among children. Recent improvements are largely due to advances in the understanding of the molecular genetics and pathogenesis of B-cell ALL, incorporation of risk-adapted therapy and the advent of targeted agents.

CCI

PFIZER CONFIDENTIAL

CT24-WI-GL03-RF02 3.0 Non-Interventional Statistical Analysis Plan for
Primary Data Collection Study
Page 4 of 17

CCI

Before the approval of BESPONSA® in Korea, this non-interventional study is designated as a Post-Marketing Surveillance (PMS) Study and is a commitment to Ministry of Food and Drug Safety (MFDS), as a part of Risk Management Plan (RMP) which is required by MFDS. The safety and effectiveness information of BESPONSA® will be gathered at minimum 100 subjects administered in the setting of routine practice in Korea during the initial 6 years after the approval.

2.1 STUDY DESIGN

This is a prospective, observational, non-interventional, multi-center study in which subjects will be administered as part of routine practice at Korean health care centers by accredited physicians. The study can be performed in Korean health care centers where BESPONSA® is prescribed to treat the relapsed or refractory B-cell precursor ALL.

All subjects enrolled should meet the usual prescribing criteria for BESPONSA® as per the local product document (LPD) and should be entered into the study at the physician's discretion.

Duration of the Study

According to MFDS re-examination regulation, the re-examination report based on collected data of 6 years must be submitted to MFDS within 3 months after the end of specified re-examination period (from the product approval date to 6 years afterwards).

The data collection period of this study is until the required subject number (100 patients) is collected. The observation period for each subject is from initiating administration of first dose of BESPONSA® to the end of the observation period of the study, which must include at least 28 calendar days following the last administration of a BESPONSA®. In case of patient that Hematopoietic Stem Cell Transplant (HSCT) after administrated BESPONSA®, follow-up until 180 days after transplantation. All the data collected during the observation period should be recorded in the case report form (CRF). In case of an adverse event/safety event recognized after the observation period ends, it should be recorded in the CRF.

Sample Size

CCI

CCI

period. CCI

100 subjects will be collected during re-examination

2.2 STUDY OBJECTIVES

The objectives of this study are to determine any problems or questions associated with BESPONSA® after marketing, with regard to the following clauses under conditions of general clinical practice, in compliance with the regulation "Re-examination Guideline of

PFIZER CONFIDENTIAL

CT24-WI-GL03-RF02 3.0 Non-Interventional Statistical Analysis Plan for
Primary Data Collection Study
Page 5 of 17

New Drugs, Etc" (Ministry of Food and Drug Safety Notification 2015-79, 2015.10.30, amended).

1. *Serious adverse event/adverse drug reaction*
2. *Unexpected adverse event/adverse drug reaction that has not been reflected in the approved drug label.*
3. *Known adverse drug reaction*
4. *Non-serious adverse drug reaction*
5. *Other safety and effectiveness information*

3. INTERIM ANALYSES

As required by MFDS regulations, the periodic interim report along with RMP report would be submitted to MFDS every 6 months for the first two years and then annual report would be submitted to MFDS for the third, fourth and fifth year. The final report would be submitted in the sixth year refer to RMP milestone.

All data collected will be integrated and reported in the sixth re-examination report.

Periodic report	Surveillance period	MFDS Submission Timeline
1-1st	2019-01-03 ~ 2019-07-02	2019-09-02
1-2nd	2019-07-03 ~ 2020-01-02	2020-03-02
2-1st	2020-01-03 ~ 2020-07-02	2020-09-02
2-2nd	2020-07-03 ~ 2021-01-02	2021-03-02
3rd	2021-01-03 ~ 2022-01-02	2022-03-02
4th	2022-01-03 ~ 2023-01-02	2023-03-02
5th	2023-01-03 ~ 2024-01-02	2024-03-02
Re-examination report	2024-01-03 ~ 2025-01-02	2025-04-02

4. HYPOTHESES AND DECISION RULES

There is no formal research hypothesis for this study. The purpose of the study is to assess real-life safety and effectiveness of BESPONSA® in Korean adult patients with relapsed or refractory B-cell precursor acute lymphoblastic leukemia (ALL) using the descriptive statistics. For the exploratory analysis, statistical tests may be performed. P-values may be provided, but no definite conclusions will be made based on p-values and no adjustments for multiplicity will be applied.

5. ANALYSIS SETS/POPULATIONS

The study requires enrolling patients aged 19 years or older who are diagnosed with relapsed or refractory B-cell precursor acute lymphoblastic leukemia (ALL) and meet all the following inclusion and exclusion criteria.

Inclusion criteria:

1. *Patients diagnosed as relapsed or refractory B-cell precursor lymphoblastic leukemia (ALL).*

2. *Evidence of a personally signed and dated informed consent document indicating that the patient (or a legally acceptable representative) has been informed of all pertinent aspects of the study.*

Exclusion criteria:

1. *Any patients who does not agree that Pfizer and companies working with Pfizer use his/her information.*
2. *Patients to whom BESONSA® is contraindicated as per the local labeling.*

5.1 SAFETY ANALYSIS SET

The safety analysis set includes patients who have been administered BESONSA® at least once and evaluated with safety-related endpoints at least once.

Patients meeting any of the following criteria will be excluded in the safety analysis set.

1. Patients who received BESONSA® prior to site initiating contract date
2. Patients who didn't receive BESONSA®
3. Safety follow-up failure: Patients without documented evidence for whom adverse event status was evaluated(Patients with "Whether AE status was evaluated" checked as No in the eCRF OR no answer is provided to question "Whether a patient has AE" in the eCRF)
4. Patients who violated inclusion/exclusion criteria
5. Patients who violated usage
6. Patients who have enrolled twice or more (i.e. if a patient has been assigned to two or more subject ID or CRFs, only one record clarified by site will be used for analysis and the others will be excluded)

5.2 EFFECTIVENESS ANALYSIS SET

The effectiveness analysis set includes patients who have been administered BESONSA® at least once and evaluated based upon effectiveness endpoints.

Patients meeting any of the following criteria will be excluded in the effectiveness analysis set.

1. Patients who are not included in safety analysis set
2. Patients who do not have any response evaluation

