7. HANDLING OF MISSING VALUES

There are no plans for imputation of missing values for variables; all missing values will be excluded from corresponding analyses. The impact of missing data will be evaluated as appropriate.

However, if the causality of the study drug on adverse event is missing, it will be considered 'related' and classified as adverse drug reaction(ADR).

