8.2.3 Effectiveness Analyses

The effectiveness analyses will be performed for Effectiveness analysis set.

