8.2.3.2 Last effectiveness

In order to identify last effectiveness of BESPONSA®, the 'effectiveness' is judged as follows based on the final effectiveness evaluation or the last cycle response evaluation(if the final evaluation is missing) and summarized by the number of subjects(n), percentage(%) and 95% confidence interval of percentage.

- Effective: CR, CRI
- Ineffective: Refractory disease, Progressive disease, Relapsed disease

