8.2.3.5 Effectiveness(Best overall response)

In order to identify effectiveness (best overall response) of BESPONSA®, the 'effectiveness' is judged as follows based on the best overall response during evaluation and summarized by the number of subjects(n), percentage(%) and 95% confidence interval of percentage.

- Effective: CR, CRI
- Ineffective: Refractory disease, Progressive disease, Relapsed disease

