8.2.3.5 Progression-free survival (PFS)

PFS is defined as time from date of enrollment to earliest date of the following events:

PFIZER CONFIDENTIAL

CT24-WI-GL03-RF02 3.0 *Non-Interventional Statistical Analysis Plan for Primary Data Collection Study*
Page 14 of 17

- Death
- Refractory disease
- Progressive disease
- Relapsed disease

Subjects without a PFS event at time of analysis will be censored at the last valid disease assessment. In addition, subjects with documentation of an event after an unacceptably long interval (>28 weeks if there was post-baseline disease assessment, or >12 weeks if there was no post-baseline assessment) since the previous disease assessment will be censored at the time of the previous assessment (date of enrollment if no post-baseline assessment). Post-study treatment follow-up disease assessments will be included.

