8.2.3.6 Overall Survival (OS)

OS is defined as the time from date of enrollment to death due to any cause. For patients last known to be alive, OS will be censored at date of completion/discontinuation.

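### Both response rates leave never-evaluated patients out of the denominator, and PFS and OS name no analysis set, so deaths before any evaluation may drop out

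*SAP*

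**What the plan says.** SAP 5.2 builds the effectiveness set from the safety set and then excludes "Patients who do not have any response evaluation". The reason for the missing evaluation plays no part. SAP 8.2.3 opens with "The effectiveness analyses will be performed for Effectiveness analysis set".

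Two response rates follow, each with a percentage and a 95% confidence interval. Last effectiveness (SAP 8.2.3.2) is judged "based on the final effectiveness evaluation or the last cycle response evaluation(if the final evaluation is missing"; best overall response is judged "based on the best overall response during evaluation". Both allow only effective or ineffective, with no category for patients not evaluated. SAP 7 plans no imputation: "all missing values will be excluded from corresponding analyses". It says the impact of missing data will be assessed where appropriate, but names no method.

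The PFS and OS clauses, whose section numbers repeat those of earlier clauses, do not name an analysis set. SAP 1 records that "Analysis for publication is added to effectiveness analyses section". For survival, "OS is defined as the time from date of enrollment to death due to any cause", and PFS also starts at enrollment and counts death. For an event that follows too long a gap, the PFS clause says the patient "will be censored at the time of the previous assessment (date of enrollment if no post-baseline assessment"). The gap allowed is 12 weeks when there has been no post-baseline assessment.

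Protocol 7.7 also defines the effectiveness group as evaluated subjects. Protocol 7.3.7 has the CRF record why a final evaluation was not done: death, loss to follow-up or other.

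**The concern.** A patient who is treated and dies before the first response evaluation has no documented response. Under SAP 5.2 that patient leaves the denominator and does not count against the rate. The evaluated-only rate equals the safety-set rate only if never-evaluated patients would have responded as often as evaluated ones. That is doubtful in a disease for which Protocol 5 gives a median survival of about 3 to 6 months in adults, and where the CRF itself lists death as a reason for no final evaluation. SAP 4 states no hypothesis, so the rates and their intervals are the effectiveness result.

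For PFS and OS there are two problems:

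- **Selection.** If the effectiveness set applies, entry to the analysis depends on having lived long enough to be evaluated, although the clock starts at enrollment and death is an event.
- **Ambiguity.** The PFS clause has a rule for patients with no post-baseline assessment, which suggests they were meant to be included. Two analysts could choose different sets and draw different curves.

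**Working it through.** **Which set applies.** For the two response rates the chain is explicit: SAP 5.2 defines the set and SAP 8.2.3 applies it. For PFS and OS it is an inference: the clauses name no set, but SAP 1 places them in the effectiveness section, so the opening sentence of SAP 8.2.3 governs by default.

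Set that default against the PFS clause. A death within 12 weeks of enrollment with no assessment is a PFS event under the clause. SAP 5.2 removes the same patient. Inside the effectiveness set the no-assessment rule has little left to act on, mainly a first evaluation that is itself the late event. The passages do not strictly contradict each other, but they fit poorly. Duration of remission is unaffected, because responders are evaluated by definition.

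**Inputs.** The plan states no response rate and no number of unevaluated patients, so there is no figure to reproduce. From the documents: 100 subjects planned (Protocol 7.4) and Clopper-Pearson 95% intervals (SAP 8.1.3). Assumed: N = 100 in the safety set, and the values of r, d and e below.

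**Response rates.** The reported rate is r/(N − d). The comparator is p = r/N, with never-evaluated patients counted as non-responders. With f = d/N, the ratio is 1/(1 − f) and the difference in percentage points is 100·p·f/(1 − f).

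| Never evaluated (f) | Ratio | p = 40% | p = 60% | p = 80% |
|---|---|---|---|---|
| 5% | 1.053 | +2.1 | +3.2 | +4.2 |
| 10% | 1.111 | +4.4 | +6.7 | +8.9 |
| 20% | 1.250 | +10.0 | +15.0 | +20.0 |

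With r = 60 and N = 100:

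- d = 0: 60/100 = 60.0% (49.7 to 69.7)
- d = 5: 60/95 = 63.2% (52.6 to 72.8)
- d = 10: 60/90 = 66.7% (55.9 to 76.3)
- d = 20: 60/80 = 75.0% (64.1 to 84.0)

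The smallest d at which the reported interval lies wholly above r/N is 16 for r = 60 (60.5 to 80.8; at d = 15 the lower limit is 59.7), 23 for r = 40 (40.3 to 63.5) and 10 for r = 80 (80.5 to 94.5).

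**Survival.** Let e be the number who die after enrollment and before any evaluation, so e ≤ d. With no censoring before t, and t later than those deaths, dropping them changes the denominator from N to N − e. The curve then shows S(t)/(1 − e/N). A true 50% appears as:

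- e/N = 2%: 0.50/0.98 = 51.0%
- e/N = 5%: 0.50/0.95 = 52.6%
- e/N = 10%: 0.50/0.90 = 55.6%

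A Kaplan-Meier check on 200,000 simulated patients gave a ratio of 1.111 for e/N = 10% with no other early loss. It gave 1.054 for 5% with another 5% lost alive before evaluation, and 1.021 for 2% with 8% lost alive. Patients lost alive add almost nothing; e drives the effect. For PFS, only unevaluated deaths within the 12-week limit count, since later ones are censored at enrollment anyway. The effect is also smaller where patients enroll after treatment has started, which Protocol 9.2 allows for.

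**The case against.** The strongest reply is that the SAP does what the protocol says. Protocol 7.7 defines the effectiveness group as evaluated subjects, Protocol 7.9 says the design is set by regulation, and effectiveness is only part of the fifth objective. All of this is true. It makes the point a design weakness and not a departure from the protocol, and it limits its weight. It does not supply the missing rate, and Protocol 7.7 lets the SAP modify the protocol's plans.

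Second, the omission may be visible. SAP Table 1 is patient disposition, and deaths of safety-set patients appear as Grade 5 events in the adverse event tables. A reader with both set sizes could compute r/N. But the table shell is not shown, and none of these tables gives a response rate or interval that includes the patients left out.

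Third, the size is hypothetical. Only patients with no evaluation at all are lost, since a missing final evaluation falls back to the last cycle. At d = 5 the shift is 3.2 points against an interval about 20 points wide. The comparator is also the lowest rate compatible with the data. This stands: the ranges show sensitivity and do not estimate the bias.

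Fourth, the SAP never says that PFS and OS use the effectiveness set. It sets them apart as manuscript analyses, and the no-assessment rule points towards inclusion. This also stands as far as it goes. What is certain is that no set is named; the loss of early deaths follows from the default reading.

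**Conclusion.** The concern holds and should be fixed; its weight is moderate. For the response rates it rests on explicit text: both use evaluated patients only, and no planned analysis includes the rest. The overstatement relative to the safety-set rate is exactly 1/(1 − d/N), provided never-evaluated patients are counted as non-responders. At an assumed 60% rate that is 3.2 points if 5% are never evaluated and 6.7 points if 10% are.

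For PFS and OS the established defect is the missing analysis set. If the default reading is followed, a 50% survival probability would be shown as 51.0% to 55.6% when 2% to 10% of patients die unevaluated, assuming no censoring before that time. The documents give neither d nor e, so the true size is unknown.

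**What to change.** 1. For last effectiveness and best overall response, add the rate over all safety-set patients, with never-evaluated patients counted as non-responders, beside the evaluated-only rate of Protocol 7.7. Label it a safety-set rate and not an all-treated rate, because SAP 5.1 also removes safety follow-up failures and usage violations.
2. Report the number never evaluated, split by CRF reason (death, loss to follow-up, other). Head the split *reason for no final evaluation*, because that is what Protocol 7.3.7 records; it does not explain why individual cycle evaluations were missed.
3. State in the PFS and OS clauses that they are run on the safety analysis set, so that the rule for patients without a post-baseline assessment has patients to apply to. The same SAP 5.1 exclusions apply here and should be noted with the results.

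The cost is SAP wording, one extra column and one count per response table. No new data are needed: undone cycle evaluations (Protocol 7.3.6) and the reason for no final evaluation are already on the CRF. The downside is less favourable figures, and a safety-set rate that is conservative where evaluations are missing for reasons other than death or treatment failure. Showing both rates lets the reader judge.
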